5.7 Other Analyses

5.7.1 Other endpoints and/or parameters

5.7.1.1 Pharmacokinetics

The plasma concentrations of Zilucoplan and its two major metabolites (████████) will be summarized by IMP and by scheduled sampling day for the PK-PPS using n, arithmetic mean, median, SD, minimum, maximum, geometric mean, geometric coefficient of variation (geoCV) and 95%CI (assuming log-normally distributed data).

A spaghetti plot of combined individual concentration versus time profiles will be presented by analyte in linear and semi-logarithmic scale with all participants overlaid on the same plot.

Additionally, Mean (+SD) plasma concentration versus time overlaid for both analytes will also be presented for all scheduled timepoints on a linear and semi-logarithmic scale. The SD will not be provided on the semi-logarithmic scale.

All figures will include the lower limit of quantification (LLOQ) on the semi-logarithmic plots.

The following rules will apply for PK data listings and summaries:

- Values below the LLOQ will be reported as below the limit of quantification (BLQ)

- Descriptive statistics of concentrations will be calculated if at most 1/3 of the individual data points at a timepoint are missing or are not quantifiable (<LLOQ). Values that are BLQ will be replaced by the numerical value of the LLOQ/2 in this instance.
- The 95% CI lower and 95% CI upper should be left blank if the SD (or equivalently, the geoCV) is 0
- The geoCV will be calculated using the following formula where SD is the standard deviation from the log-transformed data

$$\text{geoCV}(\%) = \sqrt{\exp(\text{SD}^2) - 1} \times 100.$$

Individual concentrations will be listed by IMP for the PK-PPS and will include the actual sampling time in days relative to the previous dose the ADA titer observed for the binding assay and the NAb titer for the same visit and CK change from baseline for the corresponding visit.

Summary statistics (mean, SD, median, minimum, maximum, geometric mean and geometric CV%) will be produced for each PK parameter for each analyte.

The results of the PK will be reported separately from the main clinical study report analyses and therefore analysis will not be stated at the current document.

Plasma concentration data of Zilucoplan may be subject to population pharmacokinetic analysis to derive population estimates of PK parameters and test the effect of various covariates such as anti-drug antibodies, age, weight, gender. Details of the analysis will be described separately. This analysis may be performed by combining the data from the current study with data from other Zilucoplan studies, if deemed appropriate. The results of the population PK analysis will not be reported in the study CSR but in a separate modeling report.

5.7.1.2 Pharmacodynamics

Pharmacodynamic analyses will be performed on the PD-PPS. The pharmacodynamic endpoints include sRBC lysis assay and C5 levels.

Summary statistics based on observed data will be provided for the values, change from baseline, and percent change from baseline at each of the scheduled assessment time point.

The change from baseline for each of these endpoints will be assessed by an ANCOVA model with treatment as a factor and the corresponding baseline value as covariate. The active dose will be compared to the placebo group based on the ANCOVA model; corresponding 90%CIs will be produced.

Population PD or population PK/PD analyses may be conducted for the PD variables of interest. Details of such PD or PK/PD analyses will be described separately. The results of the analyses will not be reported in the study CSR but in a separate modeling report.

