5.4 RATIONALE FOR THE CURRENT STUDY

There is substantial pre-clinical and clinical evidence supporting a role for the terminal complement cascade in the pathogenesis of IMNM (Cong 2014) (Y. e. Allenbach 2018). 80% of anti-SRP and 100% of anti-HMGCR autoantibodies are of the IgG1 immunoglobulin subclass which efficiently activates the classical pathway of complement (Anquetil 2019). These autoantibodies bind to skeletal muscle and the immune complex formed by the autoantibody-antigen interaction is recognized by the initiating component of the classical complement pathway, the C1 complex. Binding of the C1 complex leads to a series of enzymatic cleavage steps culminating in the cleavage of C5 into C5a and C5b and deposition of MAC onto the sarcolemma, a characteristic finding in IMNM muscle biopsies (Y. e. Allenbach 2018).

This uncontrolled and inappropriate activation of the classical complement cascade in muscle tissue is thought to lead to the characteristic histopathological findings and ultimately clinical weakness in patients with IMNM. Inhibition of the terminal complement pathway by zilucoplan is expected to prevent MAC deposition; to attenuate cell injury; reduce muscle cell derived creatine kinase in plasma; and potentially attenuate or even reverse clinical manifestations of IMNM.

The compelling treatment effect observed with zilucoplan in patients with anti-AChR positive gMG (Section 5.3.2.1), a similar disease which shares with IMNM autoantibody-driven hyperactivation of the classical complement pathway in skeletal muscle, supports the evaluation of zilucoplan as a potential therapy for IMNM in the present study.

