5.4.3 DOSE SELECTION AND PRESENTATION

The dose of 0.3 mg/kg was selected for this study based on its superior efficacy, greater inhibition of the terminal complement pathway, and similar safety profile as compared with the 0.1 mg/kg and placebo arms in the completed Phase 2 studies in patients with myasthenia gravis and PNH.

In the Phase 2 Study in gMG patients (RA101495-02.201), the magnitude and speed of improvement on the primary (QMG) and key secondary (MG-ADL) endpoints were greater with the 0.3 mg/kg dose than the 0.1 mg/kg dose, and both active doses were superior to placebo (see Investigator's Brochure for additional details).

The dose response seen in the clinical outcome measures is consistent with the known pharmacodynamic effect of zilucoplan that resulted, as expected, in rapid, sustained and complete (97%) inhibition of the terminal complement pathway in all gMG patients receiving the 0.3 mg/kg dose while the 0.1 mg/kg group achieved only submaximal (88%) inhibition of the terminal complement pathway.

There was no apparent difference with respect to the pattern and distribution of adverse events or tolerability between the zilucoplan treated and the placebo groups. No dose response in the safety profile was seen between the 0.1 mg/kg and 0.3 mg/kg zilucoplan groups.

Similarly, in the Phase 2 studies in patients with PNH (RA101495-01.201, RA101495-01.202, and RA101495-01.203), the starting dose of 0.1 mg/kg daily tested did not consistently achieve complete inhibition of complement activity in the sRBC lysis assay. The 0.3 mg/kg daily dose, by contrast, consistently achieved complete inhibition in the sRBC lysis assay ($\geq 95\%$ inhibition at trough) and reduced LDH to levels similar to those observed in patients receiving eculizumab. It is expected that the same pharmacodynamic response to zilucoplan as seen in patients with MG and PNH, i.e. complete complement inhibition, will drive the therapeutic response in patients with IMNM. Therefore, the well-understood and extensively-tested dosing regimen for PNH and MG, i.e. 0.3 mg/kg daily dosing with three weight brackets, has again been selected for use in this study.

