5 STATISTICAL ANALYSES

5.1 General Considerations

- Descriptive statistics for continuous endpoints will include number of participants with available measurements (n), mean, standard deviation (SD), median, 25% and 75% percentiles, minimum and maximum. Confidence Intervals (CIs) will be provided where appropriate. In general, all study endpoints will be summarized descriptively by IMP and overall (if applicable).
- Frequencies and percentages will be presented by IMP for categorical and ordinal variables. Unless otherwise noted, the denominator for percentages will be based on the number of participants included in the respective analysis set.

Participants with missing data can generally be accounted for using the following approaches:

- For summaries of demographics and baseline characteristics: summarize percentages based on all participants in the analysis set and include a “Missing” category (corresponding to participants with missing data for the variable being summarized) as the last row in the list of categories being summarized. Percentages are associated with the missing row so that percentages sum to 100.
- For summaries of efficacy and safety variables, unless otherwise specified: summarize percentages based only on those participants with observed data for the variable being summarized. As the denominator may be different from the number of participants in the

analysis set being considered, the denominator should be displayed in the table. The general format for displaying this will be “n/Nsub (%).”

All percentages will be displayed with one decimal place. No percentage will be displayed for zero counts and no decimals will be presented when the percentage is 100%. If there are no missing data for a variable, then the missing row can be removed for that variable in the shell. If there are no observations in any specific eCRF-specified category, then retain that row and present 0's across the table. E.g., if there are no 'American Indian/Alaskan native' participants in the study but this was one of the Racial Group categories in the eCRF, then retain the row and populate it with 0 values.

Decimal places for descriptive statistics will always apply the following rules:

- “n” will be an integer;
- Mean, SD, and percentiles will use one additional decimal place compared to the original data reported;
- CV [%] will be presented with one decimal place;

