5.4.3 Main analytical approach

Analysis to determine the OR and the 95%CI of ACR/EULAR ≥ 20 (minimal treatment response) between IMPs will be performed via binary logistic regression with IMP and strata as fixed factors. Bar charts by treatment will be created to illustrate the treatment effect.

In order to assess secondary efficacy for any continuous parameter, a separate linear mixed effect model will be employed for each secondary continuous efficacy parameter. At each linear mixed effect model, the response variable will be the change from baseline to Week 8. Treatment and strata will be fitted as fixed factors whereas baseline levels of the parameter as covariate; participants will be fitted at random. The Kenward-Roger approximation will be used to estimate the denominator's degrees of freedom. The least squares means (LSMs) of each IMP and the least squares mean differences (LSMDs) between the Zilucoplan and placebo will be reported for the Week 8 change from baseline along with the corresponding 2-sided 95% CIs and p-values.

Statistical estimators based on Least Square Means (LSMs) and Standard Errors (SE) or 95% CIs will be plotted for each treatment.

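### The exploratory PD ANCOVA leaves out the antibody stratum used in randomisation; this causes no bias but can widen its 90% intervals

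*SAP*

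**What the plan says.** SAP 5.7.1.2 defines the PD analysis on the PD-PPS: "The pharmacodynamic endpoints include sRBC lysis assay and C5 levels". The change from baseline in each "will be assessed by an ANCOVA model with treatment as a factor and the corresponding baseline value as covariate". Active is compared with placebo from that model, and "corresponding 90%CIs will be produced". No stratum term and no unequal-variance method is named.

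The same section also plans descriptive output: "Summary statistics based on observed data will be provided for the values, change from baseline, and percent change from baseline", at every scheduled time point. SAP 5.1 defines the descriptive statistics to include "mean, standard deviation (SD), median, 25% and 75% percentiles, minimum and maximum".

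Randomisation is stratified by antibody status (anti-HMGCR+ versus anti-SRP+; SAP 1.2). The stratum enters the Van Elteren test (SAP 5.3.2), the log10 CK and CK-response models (5.3.4), the ACR/EULAR logistic model and the models for the continuous secondary endpoints (5.4.3): "Treatment and strata will be fitted as fixed factors whereas baseline levels of the parameter as covariate".

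On the expected PD response, Protocol 5.4.3 reports 97% inhibition at 0.3 mg/kg in the gMG study and at least 95% at trough in the PNH studies. It expects that "complete complement inhibition, will drive the therapeutic response in patients with IMNM".

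**The concern.** A factor used to stratify randomisation would normally be carried into the between-arm model. The SAP does so elsewhere and gives no reason for leaving it out here. If antibody type predicts the PD change after baseline adjustment, its effect stays in the residual and the 90% intervals are wider than the data require. Protocol 5.4 makes a link conceivable: "80% of anti-SRP and 100% of anti-HMGCR autoantibodies are of the IgG1 immunoglobulin subclass which efficiently activates the classical pathway of complement".

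Two smaller matters concern sRBC lysis. An ordinary ANCOVA pools the variance, whereas near-complete inhibition would leave little scatter on zilucoplan and normal scatter on placebo. And the plan does not count how many participants reach a stated level of inhibition, although the dose rationale rests on complete inhibition.

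At stake is the precision and readability of an exploratory analysis. No hypothesis in SAP section 2 involves a PD endpoint.

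**Working it through.** **Inputs.** From the documents: 12 per arm, 1:1 (Protocol synopsis); model terms treatment and baseline, 90% interval (SAP 5.7.1.2); stratified randomisation (SAP 1.2). The plan gives no precision figure for the PD comparison, so there is none to reproduce. It gives no PD standard deviation and no stratum effect either; these are assumptions, shown as ranges. The unit is the placebo residual SD.

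**1. Cost of omitting the stratum, by formula.** The interval width is 2 × t(0.95, df) × s × √c, where c depends on the arm sizes and the baseline. Suppose the strata are evenly filled and differ by d. The omitted term leaves 24 × (d/2)² = 6d² in the residual sum of squares. With df = 24 − 3 = 21, the residual variance rises from 1 to 1 + 6d²/21, so the width is multiplied by √(1 + 6d²/21):

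- d = 0.5: √1.071 = 1.035
- d = 1: √1.286 = 1.134
- d = 2: √2.143 = 1.464

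With strata split 18:6 the sum of squares is 24 × 0.75 × 0.25 × d² = 4.5d², and at d = 1 the factor is √1.214 = 1.10.

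**2. The same by simulation** (5,000 trials per row, 12 v 12, equal variances, even strata, effect in both arms):

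| Stratum effect (SD) | Width, planned model | Width, with stratum | Coverage, planned model |
|---|---|---|---|
| 0 | 1.42 | 1.42 | 90.5% |
| 0.5 | 1.46 | 1.42 | 91.0% |
| 1 | 1.61 | 1.43 | 93.9% |
| 2 | 2.07 | 1.43 | 98.0% |

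At 1 SD, 1.606 / 1.427 = 1.125, so the planned interval is about 13% wider; equivalently, adding the stratum cuts it by 11%. With the stratum in the model, coverage is about 90% in every row. With no effect, the extra term costs about 0.3% in width.

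**3. If zilucoplan values sit at a floor.** The stratum can then shift only the placebo arm. Simulations with a 1 SD effect in placebo alone and little active-arm scatter give a reduction of about 4 to 5%. One example on the lysis scale is 14.99 to 14.41 points: 14.41 / 14.99 = 0.961.

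**4. Pooled variance for sRBC lysis.** Assumed active/placebo SD ratio 0.1 to 0.3, no stratum effect, nominal 90% interval:

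| Active v placebo in PD-PPS | Planned model | HC3 robust errors |
|---|---|---|
| 12 v 12 | 88.6–89.0% | 90.8–90.9% |
| 12 v 9 | 83.5–83.9% | 90.3–90.7% |
| 9 v 12 | 92.4–92.6% | 91.5% |

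The error is about one point at the planned sizes. It is anti-conservative only if placebo participants are lost, and conservative if active ones are.

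**5. What the planned summaries show about inhibition.** Nine participants at 98% and three at 60% give a mean of (882 + 180)/12 = 88.5%. The planned table would also show a lower quartile of 79% and a minimum of 60%, so the shortfall is visible. Ten at 99.5% and two at 84.5% give (995 + 169)/12 = 97.0%. Here the lower quartile is 99.5% and only the minimum shows that someone fell short; the number who did is not tabulated. In the first example a count would read 9/12 = 75% (exact 95% CI 43 to 95%).

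**The case against.** The strongest reply is that nothing turns on this. PD is exploratory, Protocol 12.2.6.1 plans only descriptive PD summaries, and no alpha or decision rule uses these intervals. The difference from placebo in sRBC lysis should be very large: under one set of assumed values, an interval about 15 points wide surrounds a difference of about 82. The size of any stratum effect is also undocumented. The IgG1 statement concerns autoantibodies that bind muscle and does not say that sRBC lysis or C5 differs by antibody type. And the floor argument weakens the stratum argument, because values at a floor cannot shift. All of this stands. It limits the point to consistency and precision, but gives no reason to omit a term that costs almost nothing.

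A reader might go further and infer three things that the documents do not support.

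- That a mean cannot show whether participants were fully inhibited, so that a negative CK result could not be traced to incomplete or to ineffective blockade. The planned median, quartiles, minimum and maximum of values and percent change at each visit would show incomplete inhibition. Only the count is missing.
- That the 90% intervals are miscalibrated. At 12 v 12 coverage is about 89%, and the direction of any larger error depends on which arm loses participants. No passage predicts that. For C5 levels the documents give no basis for a floor.
- That at least 95% inhibition is a target of this trial. Protocol 5.4.3 quotes it from the PNH studies and states an expectation; no PD threshold or responder endpoint is set.

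**Conclusion.** The point holds as an inconsistency with a small, one-directional cost. The PD ANCOVA omits the randomisation stratum that the SAP's other between-arm models carry. Under stratified 1:1 allocation this gives no bias. The 90% interval is about 13% wider than necessary at an assumed 1 SD stratum effect with even strata and equal variances; the loss is smaller if zilucoplan values sit at a floor, and absent if the stratum has no effect. The variance question is secondary, applies to sRBC lysis only, and matters mainly if the PD-PPS arms become unequal: coverage is about 83% at 12 active v 9 placebo and about 93% at 9 v 12, against about 89% at 12 v 12. All these figures rest on assumed SDs. No primary or secondary conclusion is affected.

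**What to change.** In SAP 5.7.1.2, add antibody stratum as a fixed factor in the PD ANCOVA, as in 5.4.3, using the value entered at randomisation, as 5.8 already does for subgroups. The cost is one degree of freedom (21 to 20 with 24 participants) and a line of wording.

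Optional, for sRBC lysis only:

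- Name a heteroscedasticity-robust or arm-specific variance for the interval. With equal variances at 12 v 12, HC3 widens it from 1.42 to 1.52 SD, so this is a trade against protection if the arms become unequal.
- Beside the planned quartiles and minimum, tabulate by visit the number and percentage of zilucoplan participants with at least 95% inhibition at trough, with an exact interval. Label it as the level quoted from earlier studies in Protocol 5.4.3, not as a target of this protocol. PD samples are already taken before dosing, so no new data are needed. Fixing the threshold before unblinding avoids a post hoc choice.

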5.8 Subgroup Analyses

The primary and continuous secondary efficacy endpoints will be summarized in ITT for the Main Portion of the study, based on the following subgroups:

- Sex (male, female)
- Age:<55 years, \geq 55 years
- Stratification factor: anti-HMGCR / anti-SRP groups (positive / negative, negative / positive)

Note: The stratification factor in the subgroup analysis will be based on the values entered into the IWRS at randomization.

The associated estimand for the subgroup analysis is defined as:

- Treatment: Zilucoplan administered by daily SC injection (0.3 mg/kg) vs matching placebo
- Target Population: is defined through the inclusion/exclusion criteria at Sections 8.1 and 8.2 of the study protocol reflecting the targeted IMNM population in the specific subgroup
- Endpoints:
 - Percentage change from baseline to Week 4 and Week 8 in CK levels;
 - At least minimal response based on (ACR/EULAR) Response Criteria Scale at Week 4 and Week 8;
 - Change from baseline to Week 4 and Week 8 in Triple Timed Up and Go (3TUG) Test (in ambulatory patients only);
 - Change from baseline to Week 4 and Week 8 in Proximal Manual Muscle Testing (MMT);
 - Change from Baseline to Week 4 and Week 8 in Physician Global Activity Visual Analogue Scale (VAS);
 - Change from baseline to Week 4 and Week 8 in Health Assessment Questionnaire (HAQ);
 - Change from baseline to Week 4 and Week 8 in MDAAT Extramuscular Disease Activity VAS Score;
 - Change from Baseline to Week 4 and Week 8 in FACIT-Fatigue Scale;
- Intercurrent event (ICE) handling: regardless of any treatment discontinuation for any reason; censoring after prohibited medication;
- Population level summary:
 - Continuous endpoints: mean change from baseline
 - Proportion of patients achieving at least minimal ACR/EULAR response

Analysis will be based only on descriptive statistics (no hypothesis testing).

5.9 Interim Analyses

No interim analysis is planned for the Main Portion of the study.

Interim analyses of the Extension Portion of the study, after Week 8 of the Main Portion of the study has been locked and unblinded, may be performed.

5.10 Data Monitoring Committee (DMC) or Other Review Board

The safety of study participants is monitored throughout the study on an ongoing basis. Given the double blind, placebo-controlled design of the study, this standard safety data review is performed while blinded to treatment assignment. If an unblinded data review should become necessary to ensure subject safety, a separate DMC will convene and evaluate study data as appropriate. To ensure the scientific integrity of the study, members of the DMC are not be directly involved in management of the study.

6 SUPPORTING DOCUMENTATION

6.1 Appendix 1: Non-key analysis specifications

6.1.1 Baseline characteristics and demographics

A separate table on demographics and baseline characteristics based on the ITT_{EXT} will be created.

- Age (years), calculated as (informed consent date – date of birth + 1)/365.25.
If day and month are missing from the date of birth, impute January 1st; if only the day is missing then impute the 1st.
- Height (cm)
- Weight (kg)
- Body mass index (BMI) (kg/m²) calculated as: BMI= "Weight (kg)" / ("Height (m)")² using the weight and height measurements obtained at screening.
- Sex (Male/Female)
- Racial Group (American Indian /Alaska native, Asian, Black, Native Hawaiian or Other Pacific Islander, White, Other/Mixed)
- Ethnicity (Hispanic or Latino, Not Hispanic or Latino)
- Years of Age (≤ 18 , $> 18 - < 55$, $\geq 55 - < 65$, ≥ 65).
- Weight in Kg (< 56 , $56 - < 77$, $\geq 77 - < 150$, ≥ 150)
- BMI in kg/m² (< 18.5 , $18.5 - < 25$, $\geq 25 - < 30$, $\geq 30 - > 40$, ≥ 40)
- Ambulatory participant (yes, no)
- Geographic region (North America, Europe)
- Countries (country 1, country2, etc.)
- Months since initial diagnosis calculated as:

$$\text{Months since diagnosis} = \frac{(\text{Date of randomization} - \text{Date of Initial IMNM Diagnosis}^1 + 1)}{30.5}.$$

¹If the date of initial IMNM diagnosis is partial, it should be imputed to the most recent feasible date (i.e., last day of the month if only day is missing, or the last day of the year if day and month are missing). Note that if the date of randomization is missing then the duration of disease will be derived using the date of screening.

- Age in years at initial diagnosis calculated as: Year of Initial IMNM Diagnosis – Year of Birth
- HMGCR SRP Antibodies (positive/negative, positive/negative),
- Muscle Biopsy performed (yes, no),
 - normal muscle biopsy
 - necrotic muscle fibers observed
 - complement C5b-9 or C9 staining performed
 - complement C5b-9 or C9 staining positive
 - complement C5b-9 or C9 staining negative
- Electromyography performed (yes, no)
 - normal electromyography
 - increased insertional activity and spontaneous fibrillations
 - abnormal myopathic low-amplitude, short-duration polyphasic motor unit potential
 - complex repetitive discharges
 - other
- MRI performed (yes, no)
 - normal MRI
 - muscle edema
 - muscle inflammation
 - muscle fibrosis
 - other
- Extramuscular Manifestations of IMNM (yes, no)
 - skin
 - cardiac
 - skeletal
 - gastrointestinal
 - pulmonary

This document contains neither recommendations nor conclusions of the FDA. It is the property of the study sponsor and is being made available to support any marketing authorization application and any extensions or variations thereof.

- constitutional
- History of any statin use (yes, no)
 - Atorvastatin
 - Fluvastatin
 - Lovastatin
 - Pravastatin
 - Pitavastatin
 - Simvastatin
 - Rosuvastatin
 - other

